## 10.7. Appendix 7: ECG Findings of Potential Clinical Concern

ECG Findings That May Qualify as AEs

 
Marked sinus bradycardia (rate <40 bpm) lasting minutes.
 
New PR interval prolongation >280 msec.
 
New prolongation of QTcF to >480 msec (absolute) or by <math>\geq</math>60 msec from baseline.
 
New-onset atrial flutter or fibrillation, with controlled ventricular response rate: ie, rate <120 bpm.
 
New-onset type I second-degree (Wenckebach) AV block of >30 seconds' duration.
 
Frequent premature ventricular complexes, triplets, or short intervals (<30 seconds) of consecutive ventricular complexes.
 

ECG Findings That May Qualify as SAEs

 
QTcF prolongation >500 msec.
 
New ST-T changes suggestive of myocardial ischemia.
 
New-onset left bundle branch block (QRS >120 msec).
 
New-onset right bundle branch block (QRS >120 msec).
 
Symptomatic bradycardia.
 
Asystole: 
 
In awake, symptom-free participants in sinus rhythm, with documented periods of asystole <math>\geq</math>3.0 seconds or any escape rate <40 bpm, or with an escape rhythm that is below the AV node.
 
In awake, symptom-free participants with atrial fibrillation and bradycardia with 1 or more pauses of at least 5 seconds or longer.
 
Atrial flutter or fibrillation, with rapid ventricular response rate: rapid = rate >120 bpm.
 
 
 
Sustained supraventricular tachycardia (rate >120 bpm) ("sustained" = short duration with relevant symptoms or lasting >1 minute).
 

- Ventricular rhythms >30 seconds' duration, including idioventricular rhythm (heart rate <40 bpm), accelerated idioventricular rhythm (HR >40 bpm to <100 bpm), and monomorphic/polymorphic ventricular tachycardia (HR >100 bpm (such as torsades de pointes)).
- Type II second-degree (Mobitz II) AV block.
- Complete (third-degree) heart block.

#### **ECG Findings That Qualify as SAEs**

- Change in pattern suggestive of new myocardial infarction.
- Sustained ventricular tachyarrhythmias (>30 seconds' duration).
- Second- or third-degree AV block requiring pacemaker placement.
- Asystolic pauses requiring pacemaker placement.
- Atrial flutter or fibrillation with rapid ventricular response requiring cardioversion.
- Ventricular fibrillation/flutter.
- At the discretion of the investigator, any arrhythmia classified as an adverse experience.

The enumerated list of major events of potential clinical concern are recommended as “alerts” or notifications from the core ECG laboratory to the investigator and Pfizer study team, and not to be considered as all-inclusive of what to be reported as AEs/SAEs.

**10.8. Appendix 8: Taste Assessment Questionnaire**

1. Questionnaire should be administered to adult participants, preferably by the trained staff. The clinical staff is trained by the CRU clinical coordinator for performing the taste questionnaire and regarding the specific study restrictions.
2. Use colored copy of the questionnaire.
3. Do not alter (reduce or enlarge) the original size of the questionnaire.
4. Please gather the following background information:

## Background Information

Study #/Study Site	
Period and Day	
Participant ID (Rand ID)	
Formulation ID	
Collection Date	
Collection Time	
Name of trained staff	
Questionnaire fully completed	Yes/No

**Example: How to provide a mark (I) on the color bar**

[figure not shown]
**Good (score = 0)**

[figure not shown]
**Bad (score = 100)**

**Questionnaire:**

[figure not shown]
**Q 1. Overall Liking – Please tell us how much you like or dislike the product you took by providing a mark (  ) on the color bar:**

[figure not shown]
**Q 2. Mouth feel – please tell us about the mouthfeel (such as grittiness, stickiness, waxiness) of the product you took by providing a mark (  ) on the color bar:**

[figure not shown]
**Q.3 Please tell us about the degree of Bitter taste of the product you took by providing a mark (X) on the color bar:**

[figure not shown]
**Q.4 Please tell us about the degree of sweet taste of the product you took by providing a mark (X) on the color bar:**

[figure not shown]
**Q.5 Please tell us about the degree of sour taste of the product you took by providing a mark (X) on the color bar:**

**Q.6 Please tell us about the degree of salty taste of the product you took by providing a mark (X) on the color bar:**

Q.7 Tongue/Mouth Burn – please tell us about the degree of tongue/mouth burn you experienced after you took the product by providing a mark (  ) on the color bar:

## 10.9. Appendix 9: Abbreviations

The following is a list of abbreviations that may be used in the protocol.

Abbreviation	Term
→	ongoing/continuous event
Abs	absolute
AD	atopic dermatitis
AE	adverse event
AIA	adjuvant-induced arthritis
ALT	alanine aminotransferase
ARA	acid-reducing agent
AST	aspartate aminotransferase
ATP	adenosine triphosphate
AUC	area under the curve
AUC 24	area under the concentration-time curve from time 0 to 24 hours
AUC inf	area under the plasma concentration-time curve from time 0 extrapolated to infinity
AUC last	area under the concentration-time curve from 0 to the time of last measurement
AUC tau	AUC from time 0 to time tau, the dosing interval
AV	atrioventricular
BA	bioavailability
BBS	Biospecimen Banking System
BCRP	breast cancer resistance protein
BID	twice daily
BLQ	below the limit of quantification
BMI	body mass index
BP	blood pressure
BUN	blood urea nitrogen
CFR	Code of Federal Regulations
CI	confidence interval
CIOMS	Council for International Organizations of Medical Sciences
CK	creatinine kinase
CKD-EPI	Chronic Kidney Disease Epidemiology Collaboration
CL/F	apparent clearance
C max	maximum observed concentration
CO 2	carbon dioxide (bicarbonate)
COVID-19	coronavirus disease 2019
CRO	Contract Research Organization
CRU	Clinical Research Unit
CSR	Clinical Study Report
CT	clinical trial

Abbreviation	Term
CYP	cytochrome P450
DAI	Dosing Administration Instructions
DC	discontinuation
DCT	data collection tool
DDI	drug-drug interaction
DILI	drug-induced liver injury
DMC	Data Monitoring Committee
DNA	deoxyribonucleic acid
EC	ethics committee
ECC	emergency contact card
ECG	electrocardiogram
eDCT	electronic data collection tool
EDB	exposure during breastfeeding
EDP	exposure during pregnancy
eGFR	estimated glomerular filtration rate
EMA	European Medicines Agency
EU	European Union
EudraCT	European Clinical Trials Database
FDA	Food and Drug Administration
FIH	first-in-human
FOB	functional observational battery
FSH	follicle-stimulating hormone
GCP	Good Clinical Practice
GERD	gastroesophageal reflux disease
GFR	glomerular filtration rate
GGT	gamma-glutamyl transferase
GLP	Good Laboratory Practice
H2	histamine-2
HBcAb	hepatitis B core antibody
HBsAb	hepatitis B surface antibody
HBsAg	hepatitis B surface antigen
HCVAb	hepatitis C antibody
HDPE	High Density Poly Ethylene
hERG	human ether-á-go-go-related gene
HIV	human immunodeficiency virus
HRT	hormone replacement therapy
IB	investigator's brochure
IC 50	50% inhibitory concentration
ICD	informed consent document
ICH	International Council for Harmonisation
ID	identity

Abbreviation	Term
IFN	interferon
IFN- $\alpha$	interferon-alpha
IFN- $\gamma$	interferon-gamma
IL	interleukin
IND	investigational new drug
INR	international normalized ratio
IPAL	Investigational Product Accountability Log
IR	immediate release
IRB	institutional review board
IV	intravenous
JAK	janus kinase
K 2 EDTA	potassium ethylenediaminetetraacetic acid
K el	first-order elimination rate constant
KDR	kinase insert domain receptor
LFT	liver function test
MAO-A	monoamine oxidase A
MATE	multidrug and toxin extrusion protein
MCH	mean corpuscular hemoglobin
MCHC	mean corpuscular hemoglobin concentration
MCV	mean corpuscular volume
MDR	medical device regulation
mRNA	message ribonucleic acid
N/A	not applicable
NADPH	nicotinamide adenine dinucleotide phosphate
NOAEL	no-observed-adverse-effect level
OAT	organic anion transporter
OATP	for organic anion transporting polypeptide
OCT	organic cation transporter
PBMC	peripheral blood mononuclear cells
PCR	Polymerase Chain Reaction
PCRU	Pfizer Clinical Research Unit
PD	pharmacodynamic(s)
PEER	Pediatric Eczema Elective Registry
P-gp	P-glycoprotein
CCI	[REDACTED]
pH	negative logarithm of hydrogen ion concentration
PI	principal investigator
PK	pharmacokinetic(s)
POC	proof-of-concept
PPI	proton pump inhibitors
PT	prothrombin time

Abbreviation	Term
QD	once daily
QTc	corrected QT
QTcF	corrected QT (Fridericia method)
qual	qualitative
R ac	accumulation ratio
rBA	relative BA
RBC	red blood cell
RNA	ribonucleic acid
SAE	serious adverse event
SAP	statistical analysis plan
SARS	severe acute respiratory syndrome
SCr	serum creatinine
SGOT	serum glutamic oxaloacetic transaminase
SGPT	serum glutamic pyruvic transaminase
SoA	schedule of activities
SOC	System Organ Class
SOP	standard operating procedure
SRSD	single reference safety document
STAT	signal transducers and activators of transcription
SULT	sulfotransferase
SUSAR	suspected unexpected serious adverse reaction
t ½	apparent terminal half-life
TB	tuberculosis
TBili	total bilirubin
TEAE	treatment emergent AE
T max	time to maximum concentration
TSLP	thymic stromal lymphopoietin
TYK	tyrosine kinase
UGT	uridine diphospho-glucuronosyltransferase
ULN	upper limit of normal
US	United States
Vc/F	apparent central volume of distribution
VEGFR	vascular endothelial growth factor receptor
Vp/F	apparent peripheral volume of distribution
WBC	white blood cell
WOCBP	woman/women of childbearing potential

1. AMENDMENTS FROM PREVIOUS VERSION(S)

None.

2. INTRODUCTION

Abrocitinib (also referred to as PF-04965842) is an orally bioavailable potent JAK1 inhibitor with good selectivity over the broader kinase being developed for the treatment of Atopic Dermatitis (AD).

The primary purpose of this study in healthy participants is to estimate the rBA of an oral suspension of abrocitinib compared to abrocitinib commercial tablet. Additionally, this study will also evaluate the effect of an acid reducing agent (ARA) on the PK of abrocitinib commercial tablet and evaluate the taste and palatability of six different oral suspensions of abrocitinib to help in guiding the selection and development of abrocitinib pediatrics formulation.

2.1. Study Design

This is a Phase 1 randomized, crossover study in healthy participants to estimate the rBA of abrocitinib oral suspension (Test formulation) compared to abrocitinib commercial tablet (Reference formulation) under fasted condition. The effect of ARA on the BA of abrocitinib and its metabolites will be evaluated by administering abrocitinib 200 mg commercial tablet with or without famotidine 40 mg as an ARA. Part B is to assess the taste and palatability of 6 different abrocitinib oral suspension formulations, to guide the selection and development of abrocitinib pediatrics oral suspension formulation.

CCI

This study consists of 2 parts, as listed below.

Part A:

This part of the study will be an open label, randomized, single dose, crossover, 3-treatment, 6-sequence, 3-periods design. Approximately 18 healthy male and/or female participants (18-55 years) will be enrolled and randomized to 1 of 6 possible treatment sequences. Participants who discontinue from the study may be replaced at the sponsor's discretion. The replacement participant will receive the same treatment sequences as the participant who discontinued. Each randomized treatment sequence will consist of 3 treatment periods as shown in Table 1 below.

Table 1. Randomized Treatment Sequences of Part A

Sequence	Period 1	Period 2	Period 3
1 (n=3)	A	B	C
2 (n=3)	B	C	A
3 (n=3)	C	A	B
4 (n=3)	A	C	B
5 (n=3)	B	A	C
6 (n=3)	C	B	A

Treatment A = Abrocitinib 200 mg commercial tablet only, under fasted conditions.

Treatment B = Abrocitinib 200 mg oral suspension formulation 1, under fasted conditions.

Treatment C = Famotidine 40 mg tablet administered 2 hours prior to abrocitinib 200 mg commercial tablet under fasted conditions.

In Period 1 through Period 3 of Part A, participants will receive a single 200 mg dose of abrocitinib commercial tablet (Treatment A), a single 200 mg dose of abrocitinib oral suspension (Treatment B), or 40 mg famotidine tablet administered 120 minutes prior to a single dose of 200 mg dose of abrocitinib commercial tablet (Treatment C) after a fast of at least 10 hours before taking the study intervention, abrocitinib. There will be at least a 72-hour washout period between each dose, ie, Day 1 of each study period (study treatment administration day) is separated by 72 hours.

Part B:

Participants who complete Part A of the study are expected to proceed to Part B. Part B will be a single-blind, randomized, 6-period, cross-over study in healthy male and/or female adult participants (18-55 years). A total of 18 healthy participants will be enrolled and randomized to 1 of 6 possible treatment sequences. Participants who discontinue from the study may be replaced at the sponsor's discretion. The replacement participant will receive the same treatment sequences as the participant who discontinued. Each randomized treatment sequence will consist of 6 treatment periods (Table 2).

Table 2. Randomized Treatment Sequences of Part B

Sequence	Period 4	Period 5	Period 6	Period 7	Period 8	Period 9
1 (n=3)	F1+ARA	F2+ARA	F3+ARA	F4+ARA	F5+ARA	F6+ARA
2 (n=3)	F6+ARA	F1+ARA	F2+ARA	F3+ARA	F4+ARA	F5+ARA
3 (n=3)	F5+ARA	F6+ARA	F1+ARA	F2+ARA	F3+ARA	F4+ARA
4 (n=3)	F4	F5	F6	F1	F2	F3
5 (n=3)	F3	F4	F5	F6	F1	F2
6 (n=3)	F2	F3	F4	F5	F6	F1

F1 = Abrocitinib oral suspension formulation 1 under fasted conditions.

F2 = Abrocitinib oral suspension formulation 2 under fasted conditions.

F3 = Abrocitinib oral suspension formulation 3 under fasted conditions.

F4 = Abrocitinib oral suspension formulation 4 under fasted conditions.

F5 = Abrocitinib oral suspension formulation 5 under fasted conditions.

F6 = Abrocitinib oral suspension formulation 6 under fasted conditions.

ARA = Famotidine 40 mg under fasted condition.

For any new healthy participants joining Part B only to support the achievement of the total number of 18 healthy participants enrolled or randomized in this part of the study, screening for healthy participants will be performed within 28 days prior to the first administration of the study intervention to confirm that they meet the participant selection criteria for the study.

Abrocitinib oral suspension formulations 1 to 6 for tasting will be offered to all participants in a blinded fashion. Participants randomized to Sequence 1-3 will receive famotidine (40 mg with 240 mL of room temperature water) 120 minutes before administering a single 200 mg dose of abrocitinib oral suspension formulations 1 to 6 with participants fasting for at least 10 hours before taking abrocitinib. While participants randomized to Sequence 4-6 will receive abrocitinib oral suspension formulations 1 to 6 with participants fasting for at least 10 hours before taking abrocitinib.

For participants receiving the ARA, famotidine, a 40 mg dose of famotidine tablet will be administered 2 hours before administering the study intervention with participants fasting for at least 10 hours before taking abrocitinib.

For a participant who completes both Part A and Part B of the study, the expected duration of participation from screening in Part A to the follow-up telephone contact in Part B of the study is approximately 11 weeks. While for a participant who completes only Part A or Part B of the study, the expected duration of participation from screening to the follow-up telephone contact is approximately 10 weeks. Participants who discontinue from the study may be replaced at the sponsor's discretion. The replacement participant will receive the same treatment sequences as the participant who discontinued.

A participant is considered to have completed the study if he/she has completed all periods of the study, including the last Follow-up phone call.

2.2. Study Objectives

2.2.1. Primary Objectives

- ***Part A***

- *Estimate the rBA of abrocitinib 200 mg oral suspension formulation 1 compared to the 1×200 mg of abrocitinib commercial tablet under fasting condition.*
- *Evaluate the effect of a single dose of an ARA (famotidine 40 mg) on the BA of abrocitinib 1×200 mg commercial tablet under fasting conditions.*

- ***Part B***

- *Evaluate the taste and palatability of 6 abrocitinib suspension formulations using a 200 mg dose.*

2.2.2. Secondary Objectives

CC
C
I

- *Determine the PK of metabolites (M1, M2 and M4) following the administration of 1×200 mg of abrocitinib commercial tablet with or without an ARA (famotidine 40 mg) in Part A.*
- *Evaluate the safety and tolerability following oral administration of each of the abrocitinib formulations in Parts A and B.*

CCI

3. INTERIM ANALYSES, FINAL ANALYSES AND UNBLINDING

No formal interim analysis will be conducted for this study. As this is a sponsor-open study, the sponsor may conduct unblinded reviews of the data during the course of the study for the purpose of safety assessment, facilitating PK/PD modeling, and/or supporting clinical development. After the completion of Part A (Periods 1, 2 and 3) of the study, PK analysis of Part A will be conducted, and PK tables and figures will be generated to support ongoing registrations.

4. HYPOTHESES AND DECISION RULES

4.1. Statistical Hypotheses

No formal inferential statistics will be applied to the safety data.

4.2. Statistical Decision Rules

No decision rules are required.

5. ANALYSIS SETS

5.1. Enrolled Analysis Set

All participants who sign the ICD.

5.2. Pharmacokinetic (PK) Analysis Set

5.2.1. Concentration Analysis Set

The PK concentration population is defined as all participants randomized and treated who have at least 1 concentration in at least 1 treatment period.

5.2.2. Parameter Analysis Set

The PK parameter analysis population is defined as all participants randomized and treated who have at least 1 of the PK parameters of primary interest in at least 1 treatment period.

5.3. Taste Analysis Set

All participants who receive at least 1 abrocitinib oral suspension formulation for taste evaluation and complete the abrocitinib Taste Assessment Questionnaire.

5.4. Pharmacodynamic Analysis Set

None.

5.5. Safety Analysis Set

All participants randomly assigned to study intervention and who take at least 1 dose of study intervention. Participants will be analyzed according to the product they actually received.

5.6. Other Analysis Sets

None.

5.7. Treatment Misallocations

All analyses will be performed on an “as-treated” basis and will not include data from subjects who are randomized but not treated.

If a subject takes a treatment that is not consistent with the treatment they are randomized to, for example takes a treatment out of sequence or takes the same treatment twice, then they will be reported under the treatment that they actually receive for all safety, PK and taste analyses, where applicable.

5.8. Protocol Deviations

Subjects who experience events that may affect their PK profile (eg, lack of compliance with dosing) may be excluded from the PK analysis. At the discretion of the pharmacokineticist a concentration value may also be excluded if the deviation in sampling time is of sufficient concern or if the concentration is anomalous for any other reason.

A full list of protocol deviations will be compiled and reviewed to identify major and minor deviations prior to database closure.

5.8.1. Deviations Assessed Prior to Randomization

At Screening, the investigator will assess subjects against the inclusion and exclusion criteria as set out in Sections 5.1 and 5.2 of the protocol.

5.8.2. Deviations Assessed Post-Randomization

A full list of protocol deviations for the study report will be compiled prior to database closure. Any significant deviation from the protocol will be reviewed prior to database closure and a decision taken regarding evaluation for each analysis population.

6. ENDPOINTS AND COVARIATES

6.1. Efficacy Endpoint(s)

None.

6.2. Safety Endpoints

An adverse event will be considered a Treatment-Emergent Adverse Event (TEAE) if the event started during the effective duration of treatment. All events that start on or after the first dosing day and time/start time, if collected, but before the last dose plus the lag time (28 days) will be flagged as TEAEs. The algorithm will not consider any events that started prior to the first dose date. Any events occurring following start of treatment or increasing in severity will be counted as treatment emergent.

Events that occur in a non-treatment period (for example, Washout or Follow-up) will be counted as treatment emergent and attributed to the previous treatment taken.

The following data are considered in standard safety summaries (see protocol for collection days and list of parameters):

- *adverse events;*

- *laboratory data;*
- *vital signs data;*
- *ECG results.*

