**Table 2. Schedule of Activities (Part B)**

Visit Identifier a Abbreviations used in this table may be found in Appendix 9: Abbreviations	Period 4		Period 5	Period 6	Period 7	Period 8	Period 9		Early Termination/ DC	Follow-up b
Days Relative to Day 1	Day -1 c	Day 1	Day 1	Day 1	Day 1	Day 1	Day 1	Day 2		28-35 Days

- a. Day relative to the first day of study intervention dosing in all periods.
- b. Contact may occur via telephone contact and must occur 28 to 35 days from administration of the final dose of study intervention, either in Parts A (in case of early termination/DC) or in Part B of the study.
- c. Day -1 of Period 4 in Part B of the study overlaps with Day 3 of Period 3 in Part A of the study.
- d. For new participants enrolled in Part B only, all Screening and Day -1 visit procedures will be performed as listed in [Table 1](#) SoA (Part A).
- e. A complete physical examination will be done at screening or may be deferred to Day -1 of Period 4 at the discretion of the investigator for new participants admitting for Part B only of the study. A complete physical examination should be performed on Day 2 of Period 9 or at the Early Termination/DC visit (if this occurs). A brief physical examination can be performed at other times if findings during the previous examination or new/open AE, at the discretion of the investigator.
- f. Section 8.2.4 Safety laboratory test assessments consist of hematology, urinalysis, and clinical chemistry. For details on the tests to be performed, please refer to protocol [Appendix 2](#). The safety tests will be performed at screening, Day-1 of Period 4, each admission to CRU, at study discharge, and early withdrawal. All assessments must be collected following at least a 4-hour fasting period. Samples will be collected if the reason for DC is related to an AE. Additional assessments may be performed at the discretion of the investigator.
- g. To be collected at predose of abrocitinib for new participants enrolled in Part B only.
- h. To be collected at predose and 1-hour postdose (around  $T_{max}$ ) of abrocitinib.
- i. For new participants joining this part of the study, and admitted for residence, a subsequent COVID-19 test will be performed after 4 days (ie, upon completion of  $4 \times 24$  hours in-house), or if they develop COVID-19 like symptom(s).
- j. To be done at least daily during residence.

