### **6. STUDY INTERVENTION(S) AND CONCOMITANT THERAPY**

Study intervention is defined as any investigational intervention(s), marketed product(s), placebo, medical device(s), or study procedure(s) intended to be administered to a study participant according to the study protocol.

For the purposes of this protocol, study intervention refers to study intervention.

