### 6.1.1. Administration

**Part A:** Following an overnight fast of at least 10 hours, participants will receive the study intervention, abrocitinib, at approximately 0800 hours (plus or minus 2 hours). Investigator site personnel will administer the study intervention during each period with ambient temperature water to a total volume of approximately 240 mL. Participants will swallow the study intervention whole and will not manipulate or chew the study intervention prior to swallowing. For participants receiving the ARA, famotidine, a 40 mg dose of famotidine tablet will be administered 2 hours before administering the study intervention, abrocitinib, with participants fasting for at least 10 hours before taking abrocitinib.

**Part B:** Abrocitinib oral suspension formulations 1 to 6 for tasting will be offered to all participants in a blinded fashion. Following an overnight fast of at least 10 hours, participants will receive the study intervention, abrocitinib, at approximately 0800 hours (plus or minus 2 hours). Participants will place samples into their mouths, swish the sample in the mouth for approximately 10 seconds and then swallow it. Each participant will record the sensory attributes at timed intervals of 0 (immediately after dosing), 5, 10 and 20 minutes after swallowing using the Abrocitinib Taste Assessment Questionnaire. Each formulation will be tested daily. Participants will be asked as much as possible to not verbalize their responses and not discuss taste with other participants until after they have filled out the response for that formulation in the questionnaire. Participants will cleanse their mouth with room temperature water before tasting a formulation. This water will not be swallowed. For participants receiving the ARA, famotidine, a 40 mg dose of famotidine tablet will be administered 2 hours before administering the study intervention with participants fasting for at least 10 hours before taking abrocitinib.

For both Part A and Part B of the study, participants will be instructed to fast for at least 10 hours before receiving abrocitinib. Water will be withheld for 1-hour predose and 1 hour after study treatment administration, and food will only be allowed after 4 hours postdose.

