#### **8.3.1. Time Period and Frequency for Collecting AE and SAE Information**

The time period for actively eliciting and collecting AEs and SAEs (“active collection period”) for each participant begins from the time the participant provides informed consent, which is obtained before the participant’s participation in the study (ie, before undergoing any study-related procedure and/or receiving study intervention), through and including a minimum of 28 calendar days after the last administration of the study intervention.

Follow-up by the investigator continues throughout and after the active collection period and until the AE or SAE or its sequelae resolve or stabilize at a level acceptable to the investigator.

For participants who are screen failures, the active collection period ends when screen failure status is determined.

If the participant withdraws from the study and also withdraws consent for the collection of future information, the active collection period ends when consent is withdrawn.

If a participant permanently discontinues or temporarily discontinues study intervention because of an AE or SAE, the AE or SAE must be recorded on the DCT and the SAE reported using the CT SAE Report Form.

Investigators are not obligated to actively seek information on AEs or SAEs after the participant has concluded study participation. However, if the investigator learns of any SAE, including a death, at any time after a participant has completed the study, and he/she

considers the event to be reasonably related to the study intervention, the investigator must promptly report the SAE to Pfizer using the CT SAE Report Form.

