8.3. Safety Analysis

All safety analyses will be performed on the safety population. A set of summary tables split by treatment and by Part A, Part B and Part (A+B) will be produced to evaluate any potential risk associated with the safety and toleration of administering study treatments.

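### Does SAP 6.2 leave the end of the TEAE window open, and does its attribution rule distort the tablet-versus-suspension safety tables?

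*SAP*

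**What the plan says.** SAP 6.2 opens by tying a treatment-emergent adverse event (TEAE) to onset during the effective duration of treatment. It then gives the flag: events starting on or after the first dose but "before the last dose plus the lag time (28 days) will be flagged as TEAEs". The next sentence says the algorithm ignores events that began before the first dose date. Two further statements follow. One reads "Any events occurring following start of treatment or increasing in severity will be counted as treatment emergent". The other covers non-treatment periods, with washout and follow-up as examples, and says such events "will be counted as treatment emergent and attributed to the previous treatment taken". Neither repeats the 28-day limit.

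Protocol 8.3.1 collects adverse events "through and including a minimum of 28 calendar days after the last administration of the study intervention". Protocol Table 2, note b, says the follow-up contact "must occur 28 to 35 days from administration of the final dose of study intervention".

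On presentation, SAP 8.3 states: "A set of summary tables split by treatment and by Part A, Part B and Part (A+B) will be produced". SAP 8.3.4 leaves the adverse event layout to the sponsor's reporting standards, and redacted text follows it. SAP 4.1 rules out formal inference on safety data.

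**The concern.** Three things look wrong at first.

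- **Window.** Read literally, one sentence stops TEAEs just short of day 28 and two others have no end. The contact is never scheduled before day 28 and may come as late as day 35, so events with onset in that stretch can reach the database. Day 28 itself is collected under the protocol but falls outside the SAP flag. Two programmers could report different TEAE counts from the same records.
- **Start of a treatment.** Famotidine precedes abrocitinib by 2 hours. Protocol 6 says "Study intervention is defined as any investigational intervention(s), marketed product(s), placebo, medical device(s), or study procedure(s) intended to be administered", which takes in famotidine. Protocol 6.1.1 says the "famotidine tablet will be administered 2 hours before administering the study intervention", which uses the term for abrocitinib alone. It can then seem unclear whether an event in that gap belongs to the new treatment or to the one before.
- **Pooled table.** Tablets are given only in Periods 1 to 3, and every Period 9 dose is a suspension. With attribution to the previous treatment, follow-up in participants who complete both parts always counts against a suspension. The tablet is the reference formulation and TEAEs are a secondary endpoint, so a reader comparing crude counts in the A+B table could be misled.

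**Working it through.** The documents give no participant-day figure to reproduce, so this is a direct count from the sequence tables.

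**Inputs.** Part A: 18 participants, 6 sequences of 3, each treatment given once per participant, 72 hours between doses (SAP 2.1, Table 1). Part B: 18 participants, 6 sequences of 3, one formulation a day (SAP Table 2; Protocol 6.1.1). Period 3 Day 3 coincides with Period 4 Day -1 (Protocol Table 1, note c), so the last Part A dose also carries 3 days. TEAE limit: 28 days. Latest contact: day 35. Assumption: all 18 complete both parts.

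**Disputed window**
- Inside the limit, after the last dose: 18 × 28 = 504 participant-days.
- To the latest contact: 18 × 35 = 630.
- Difference: 630 − 504 = 126, or 126/504 = 25%. This is the maximum and needs every contact to fall on day 35. If every contact falls on day 28, it is 0.

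**Attributed time, with the 28-day limit**

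| Table | Column | Calculation | Participant-days | After last dose |
|---|---|---|---|---|
| Part A | A, B, C (each) | 18 × 3 | 54 | 0 |
| Part B | F1 to F6 (each, with and without famotidine) | 15 × 1 + 3 × 28 | 99 | 84 |
| A+B | Tablet (A and C) | 54 + 54 | 108 | 0 |
| A+B | Suspensions | 54 + 6 × 99 | 648 | 504 |

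Per dose in the pooled table, the tablet has 108/36 = 3.0 days and the suspensions 648/126 = 5.1. The difference comes entirely from time after Period 9. The Part A table is even across A, B and C, and the Part B table is even across the six formulations.

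**When the 504 and 0 do not hold.** SAP 2.1 foresees participants who complete only Part A, and Protocol Table 2, note b, foresees follow-up after a final dose in Part A. Period 3 ends on A, B or C for 6 of 18 participants each. A Part-A-only participant therefore ends on a tablet in 12 of 18 cases and then adds 28 days to the tablet. The 504 also runs from the Period 9 dose, so it includes the time up to discharge on Day 2. Counted from discharge, it is about 18 × 27 = 486.

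**Famotidine gap.** Part A has 18 famotidine doses and Part B has 9 × 6 = 54, so there are 72 gaps. At 2 hours each that is 144 hours, or 6 participant-days of 108 + 648 = 756 (0.8%). The SAP attributes by treatment. Its Table 1 defines Treatment C to include the famotidine dose, and its Table 2 labels the Part B cells as formulation plus acid-reducing agent. A dosing day that has begun with famotidine is not naturally a non-treatment period, so such an event belongs to that day's treatment.

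**The case for a change.** The best case for a change is that a TEAE definition decides which records enter an endpoint, so it should admit one reading only. The sentences in tension are all visible in SAP 6.2, so no redacted text can reconcile them. The SAP does not say that the later sentences sit under the 28-day limit. The remedy would cost a few words and a footnote, and without the footnote a reader of the pooled table might not notice that tablet and suspension counts cover different lengths of time.

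Part of this stands. The SAP is silent on whether the limit governs all three sentences, and its limit leaves out day 28 while the protocol collects it. The uneven time in the pooled table is also real.

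It does not carry a change, for three reasons. First, the paragraph reads coherently as written: the flag sets the window, the sentence after the pre-dose exclusion completes it, and the last sentence tells analysts where to place an event between or after doses. Follow-up begins well before day 28, so counting follow-up events does not contradict a 28-day end. Second, the uneven time follows from the fixed order of the parts and from an attribution rule that nobody proposes to drop, and separate Part A and Part B tables are already planned. Third, the visible text does not name the Part B columns. A layout crossing formulation with famotidine would be uneven, but that is a hypothesis about tables not shown. SAP 7 and 8.3.4 leave imputation and layout to the sponsor's standards.

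**Conclusion.** No change to the plan is needed. The wording leaves a small gap that analysts would fill by applying the stated 28-day flag throughout. At most, events with onset between day 28 and the contact could move in or out of the TEAE count: 0 to 126 participant-days if all 18 complete Part B. These are days at risk, not events. Few events are expected there, because the half-life is about 3 to 5 hours and only one contact is scheduled after discharge. Such events are recorded under either reading.

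The 504-to-0 split in the pooled table is correct under two assumptions: that every participant's last dose is in Part B, and that the 28-day end applies. With follow-up to day 35 it would be 630 to 0. It affects how one descriptive table is read. The randomised tablet-versus-suspension comparison is in the Part A table, which is balanced at 54 participant-days per treatment. The primary PK and taste analyses are untouched and no safety test exists to be biased. Saying that the limit covers all three sentences, and whether day 28 is included, would be a courtesy if the SAP were reopened for another reason. No result depends on it.
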